#### **9.5 Data Analyses**

Baseline characteristics between the SUCCEED intervention and usual care groups will be compared. Continuous variable means will be compared using the t-test and ordinal or non Gaussian continuous variables will be compared using the Wilcoxon rank sum test. Unordered categorical variables will be compared using Chi-square test or Fisher's exact test.

Enrollment weights based on a logistic regression model will be calculated using demographic data collected from eligible non-participants. If needed, attrition weights will be determined from logistic regression models using demographic data on participants who drop out of the study. These two weights will be combined to form an overall weight (using the inverse of the product of the probabilities of participation). Both raw and adjusted rates using the overall weight will be compared between SUCCEED and usual care arms.

Intention to treat analyses on all primary and secondary outcomes will be conducted using ordinal logistic or multiple linear regression models, incorporating the overall weight. Intervention status will be an independent variable in all models. We will compare study outcomes between the control and intervention groups both with and without adjusting for potential covariates associated with the outcome measure.

We will test the moderator and mediator effects separately. To assess the moderating effects, we will compare regression models we fit including interaction terms between the independent variables and each possible effect modifier, and the models that do not include the corresponding interaction terms, using the likelihood ratio test (LRT). To assess the mediating effects, we will use Baron and Kenny (1986) methods to run a series of regression analysis and use the Sobel test and Bootstrapping to test mediating effects.

To check the fidelity (uptake) of the SUCCEED intervention, we will also analyze attendance at SUCCEED clinics and the number of telephone coordination of care calls made during enrollment. Because subjects will be recruited from four hospital systems, there could be some underlying intra-site correlations of outcome measures in the collected data, which will have potential impacts on statistical significant tests of parameter estimates in the analyses. To take this into account in our analyses and modeling, robust standard errors will be calculated using Huber/ White/Sandwich method to ensure valid significance testing. Although we will assess for the impact of clustering data structure, we do not expect a large intra-site correlation because the three sites are part of the same county healthcare system and we are not aware of differences of outcomes by site. Furthermore, we will also include site dummies in our model to control and evaluate the differences in parameter estimates, especially if there are significant variations among the sites.

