**Primary Objective #2:** To test the impact of a sustainable Chronic Care Model-based intervention on control of systolic blood pressure (primary outcome), composite stroke risk, and each individual stroke risk factor (secondary outcomes), among 500 adults (over 90% minority) recruited “early” - during or shortly after hospitalization for an ischemic or hemorrhagic stroke or TIA - at one of the four Los Angeles County safety net medical centers. We will conduct a randomized trial of this intervention that includes the new, community-centered component developed in aim #1, and a “re-engineered” healthcare delivery system with nurse practitioners or physician assistants as care managers, distribution of home blood pressure monitors, group clinics, and a care management software system tailored to secondary stroke prevention and interfaced with the mobile health platform used by the CHWs, relative to usual care. We will include non-English speaking individuals from Hispanic, Chinese, and Korean racial and ethnic groups, and a broad range of stroke severity. We will analyze potential moderators (age, gender, stroke type and severity, education, country of birth/primary language, diabetes comorbidity, care team composition) to understand robustness of intervention impacts across levels of individual and health system characteristics. We will conduct a formative evaluation to continuously improve implementation, and will measure and analyze extent of intervention implementation, as it is delivered for up to 12 months after stroke or TIA through transition of patients into primary care. We will analyze potential mediators (life chaos, competing needs, medication adherence, knowledge of stroke risk factors, participation in self-management programs, social isolation, depression, health literacy, engagement with healthcare provider team, attitudes/health beliefs, self-efficacy, readiness to change, perceived risk, and perceptions of quality of interactions with provider) of the intervention’s impact, using both qualitative and quantitative methods.

*Hypothesis: Patients randomized to the SUCCEED intervention will achieve 8mm greater reduction in systolic blood pressure reduction and lower stroke risk scores at 1 year versus those randomized to usual care.*

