#### 9.2.2 *Secondary outcomes*

Refer to **Table 1** provided below.

**Table 1.** Primary & Secondary Outcomes

Primary Outcome
Blood Pressure (change in blood pressure, as well as proportion of patients with BP under 120/80)
Secondary Outcomes
Risk of recurrent stroke, future cardiovascular event
Lipid profile: LDL cholesterol level, Triglyceride level, HDL cholesterol level
Hemoglobin A1c
C-reactive protein (CRP)
Adiposity: Body mass index (BMI), waist circumference, Waist-hip ratio, Waist-to-Height Ratio
Healthy Lifestyle Behaviors & Factors: Physical Activity, Diet, Smoking, Alcohol Use
Death

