### 9.3 Sample Size and Accrual

#### **Power Analysis**

Power Analyses was conducted with comparison of main outcomes (systolic blood pressure (SBP)) between the control and intervention arms. Based on availability of patients and our capacity, we plan to enroll 500 subjects from four senior centers. Using Intra-class correlation (ICC) of the four centers at 0.0085 level, attrition after the baseline between 20% to 30% level, mean SBP 141 mm Hg and standard deviation (SD) 20, three repeated measurements: baseline, 3 months, and 12 months (Brown and Prescott 2006), the underlying

statistical power of the study comes from two dimensions of observations: the number of unique subjects and the number of repeated measurements within a subject. Based on sample size and power analyses method proposed by Diggle et al. (1994) and Liu et al. (2005) for repeated measures analysis with a type I error of 0.05, type II error of 0.2 (or equivalent to power of 80%), 2.6 and 2.4 average data points for each subject (corresponding to 20% and 30% attrition respectively), and an auto-correlation at 0.2 level, the effective sample size will be 147 and 147 out of the planned 250 and 250 participants in each of the 2 arms (after adjusting for clustering effect), which will enable us to detect an effect size for SBP as small as 0.215 in standard deviation units or 4.29 mm Hg (for 20% attrition), and 0.253 in standard deviation units or 5.06 mm Hg (for 30% attrition).

The seminal work for moderator and mediator effect was from Baron and Kenny (1986). For potential moderators (e.g., age, gender, stroke type and severity, education, country of birth/primary language), we will test power of moderation using the most common measure of effect size  $f^2$  (Aiken & West, 2001), which equals the unique variance explained by the interaction term divided by sum of the error and interaction variances. Cohen (1988) has suggested that  $f^2$  effect sizes of 0.02, 0.15, and 0.35 are termed small, medium, and large, respectively. A more realistic standard for effect sizes with moderators might be 0.005, 0.01, and 0.025 for small, medium, and large, respectively.

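### Attrition weights built on demographics alone, with no primary baseline-adjusted SBP model named, leave the SBP comparison open to bias if dropout depends on SBP differently by arm

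*Combined protocol and SAP*

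**What the plan says.** Section 9.5 (Data Analyses) makes attrition weighting conditional: "If needed, attrition weights will be determined". No trigger is given. The model behind the weights is described only as follows: "attrition weights will be determined from logistic regression models using demographic data on participants who drop out of the study". These weights are multiplied with the enrollment weights. The intention-to-treat analyses of all outcomes then use "ordinal logistic or multiple linear regression models, incorporating the overall weight".

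The paragraph on outcome models adds that "Intervention status will be an independent variable in all models" and that the arms are compared "both with and without adjusting for potential covariates associated with the outcome measure". The covariates are not listed, and neither comparison is designated primary. Table 1 in Section 9.2 gives the primary outcome as "change in blood pressure, as well as proportion of patients with BP under 120/80".

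Section 9.3 plans for "attrition after the baseline between 20% to 30% level", without a split by arm. Objective 2 in Section 1.1 hypothesises that the intervention arm "will achieve 8mm greater reduction in systolic blood pressure" at one year.

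Section 9.5 contains no imputation, no missing-at-random statement and no missing-not-at-random analysis.

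**The concern.** Inverse-probability weights remove dropout bias only for variables in the weight model, or for what those variables predict. The variables most likely to link dropout to 12-month SBP are earlier SBP and stroke severity. Both are collected at baseline and at 3 months (Synopsis, Interventions and Duration), and arm is known for everyone. None of them is named for the weights.

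A difference by arm is plausible because the arms differ in contact. Section 9.4 has care coordinators monitoring risk factors in the intervention arm and telephoning about care. If poorly controlled patients leave one arm and stay in the other, completers are no longer comparable on SBP, and demographic weights will not restore the balance.

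The plan also lists change in blood pressure as the outcome and permits an unadjusted comparison. An unadjusted change score with demographic-only weights is therefore a permitted primary analysis, and it is the one most exposed to baseline-driven dropout.

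**Working it through.** **The plan's own figures, as a yardstick.** The documents give no bias figure. They give detectable differences of 4.29 and 5.06 mm Hg (Section 9.3). The formula is difference = SD × √(2(1.96 + 0.84)² f / n), with n = 147 per arm, SD 20, and f the variance factor for the mean of m visits under AR(1) correlation 0.2.
- m = 3: f = 0.431, giving 0.2146 SD = 4.29 mm Hg.
- m = 2: f = 0.6, giving 0.2531 SD = 5.06 mm Hg.

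Both reproduce, but only with m rounded to 3 and 2. The stated 2.6 and 2.4 points would give 4.56 and 4.71.

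**Inputs for the bias.**
- From Section 9.3: SD 20, correlation ρ = 0.2, loss 20-30%. I use d = 0.25, so d × SD = 5 mm Hg.
- Assumed: ρ = 0.5 as an alternative, equal correlation between all visits, and dropout log-odds of 0.35 or 0.7 per SD of SBP in one arm and zero in the other.
- In simulation, dropouts in the affected arm then lie about δ = 0.34 or 0.65 SD (7 or 13 mm Hg) above completers on the SBP that drives dropout.

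**Formulas for the size of the bias** (demographics taken as nearly uninformative about SBP):
- Unadjusted 12-month SBP, dropout driven by baseline or 3-month SBP: ρ × d × δ × SD.
- Unadjusted change score, baseline-driven: (1 − ρ) × d × δ × SD, in the opposite direction.
- Baseline-adjusted SBP, 3-month-driven: ρ(1 − ρ) × d × δ × SD.
- Baseline-adjusted SBP, baseline-driven: 0. Change score, 3-month-driven: 0 under equal correlation.

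| Analysis and driver (mm Hg) | ρ 0.2, δ 0.34 | ρ 0.2, δ 0.65 | ρ 0.5, δ 0.34 | ρ 0.5, δ 0.65 |
|---|---|---|---|---|
| Unadjusted 12-month, either driver | 0.34 | 0.65 | 0.85 | 1.63 |
| Unadjusted change, baseline-driven | 1.36 | 2.60 | 0.85 | 1.63 |
| Baseline-adjusted, 3-month-driven | 0.27 | 0.52 | 0.43 | 0.81 |
| Baseline-adjusted, baseline-driven | 0 | 0 | 0 | 0 |

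Simulations with demographic-only weights (a demographic variable correlated 0.2 with SBP) agree with these values to about 0.1 mm Hg. The ranges quoted in the verdict are rounded to allow for that. The same SBP dependence in both arms gives 0.1 or less.

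If patients with high SBP leave the intervention arm, the unadjusted 12-month comparison is flattered and the unadjusted change score is diluted. The signs reverse if they leave the control arm, or if patients with low SBP leave.

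**What the repairs achieve.** Weights with arm, baseline SBP and their interaction remove the baseline-driven bias (within 0.1). Adding 3-month SBP by arm removes the 3-month-driven bias, provided dropouts have that reading. The plan's 2.6 and 2.4 data points equal 1 + 2(0.8) and 1 + 2(0.7), so the whole loss is counted at month 3 already. Taken literally, dropouts have no 3-month SBP.

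If dropout follows the unseen 12-month SBP (30% loss, dropouts about 0.48 SD higher), the full weights reduce the bias only from 2.85 to 2.65 mm Hg at ρ = 0.2, and from 2.99 to 2.06 at ρ = 0.5.

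**Consequence for the test.** With 200 or 175 completers per arm the standard error for 12-month SBP is 20√(2/n) = 2.0 or 2.14 mm Hg. A bias of 0.6 moves the two-sided type I error from 0.05 to 0.06. A bias of 1.5 moves it to 0.11-0.12.

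**The case against.** The documents show neither SBP-related dropout nor dropout that differs by arm, and a slope of 0.7 in one arm with none in the other is a strong mechanism. Section 6.2.3 sets out retention measures and an attempt at a final outcome survey on withdrawal, both of which would reduce loss. The omission of arm from the weights is read from silence, and the weights are conditional. The plan also allows adjustment for covariates associated with the outcome. Baseline SBP is the obvious candidate, and it alone removes baseline-driven bias.

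Most of this stands, and it limits the size of the point. It does not close the gap. Baseline SBP is never named and the adjusted model is not made primary, so the protection is optional. The statement that intervention status enters all models sits with the outcome models. Even if it were extended to the attrition model, it would supply arm but not SBP.

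A reader might infer that the 12-month SBP effect will be biased by 2-3 mm Hg. The documents do not support that. Those values follow from 0.2 × 0.5 × 20 = 2.0 and 0.3 × 0.5 × 20 = 3.0, which requires dropouts to differ by an assumed 10 mm Hg on the 12-month reading itself. Better weights would largely not repair that case. Nor is it a ceiling, since a 1 SD difference gives 4.0 and 6.0. Among the mechanisms that the recorded data can address, a value near 2.7 arises only for an unadjusted change score with baseline-driven dropout.

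**Conclusion.** The point holds in a limited form. The attrition model as written omits recorded variables that matter, and the primary SBP model is not tied down. Under the assumed one-arm mechanism the bias is about 0.3-1.7 mm Hg for unadjusted 12-month SBP, about 0.3-0.9 for baseline-adjusted SBP with 3-month-driven dropout, and about 0.8-2.7 for an unadjusted change score with baseline-driven dropout. At its largest, 2.7 is 34% of the hypothesised 8 mm Hg and 53-63% of the detectable 5.06-4.29. If SBP-related dropout does not differ by arm, the bias is about 0. These sizes rest on 25% loss, SD 20, correlation 0.2-0.5 and log-odds 0.35-0.7. Only the SD, the loss range and the correlation of 0.2 come from the plan. Confidence is moderate. The change should be made because it is cheap, not because bias has been shown.

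**What to change.** In Section 9.5:

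1. Name the model adjusted for baseline SBP as the primary SBP analysis. This alone removes bias from baseline-driven dropout. Adjusted for baseline, change and 12-month SBP give the same treatment estimate.
2. Fit the attrition model on arm, baseline SBP, arm-by-baseline-SBP, NIHSS, the stratification factors (site, language, stroke type) and demographics. For losses after month 3, add 3-month SBP by arm. Alternatively, use a likelihood-based repeated-measures model on all observed SBP values. In either case, state when the weights apply instead of leaving them conditional.
3. Add a missing-not-at-random sensitivity analysis, for example shifting the assumed 12-month SBP of dropouts by a range of amounts separately by arm. Steps 1 and 2 do not repair dropout driven by the unseen 12-month value.

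The cost is SAP wording, slightly more analysis work and somewhat more variable weights. All the variables are already collected.

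### Section 9.3 bases its SBP power on a repeated-measures analysis that Section 9.5 does not specify, so the printed detectable differences do not describe the planned analysis

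*Combined protocol and SAP*

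**What the plan says.** Section 9.3 (Power Analysis) says that power comes from two sources, "the number of unique subjects and the number of repeated measurements within a subject". The method is one "for repeated measures analysis with a type I error of 0.05" and 80% power, using "three repeated measurements: baseline, 3 months, and 12 months" with "2.6 and 2.4 average data points for each subject (corresponding to 20% and 30% attrition respectively"). The other inputs are an autocorrelation of 0.2, SD 20 mm Hg, a site ICC of 0.0085 and an effective size of 147 per arm out of 250. The results are 0.215 SD (4.29 mm Hg) at 20% attrition and 0.253 SD (5.06 mm Hg) at 30%.

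Section 9.5 states: "Intention to treat analyses on all primary and secondary outcomes will be conducted using ordinal logistic or multiple linear regression models". These models carry a combined enrolment and attrition weight and are run with and without covariates; neither version is called primary. The only correlation that Section 9.5 discusses is within site, handled by Huber/White sandwich standard errors and site dummies.

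The time point and form of the outcome are spread over other sections. The hypothesis under Primary Objective #2 (Section 1.1) is an 8 mm Hg greater reduction at 1 year. Table 1 in Section 9.2.2 lists change in blood pressure and the share of patients below 120/80, with no time point.

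**The concern.** A power statement is informative only for the analysis that will be run. Here the calculation takes credit for several readings per patient, while the analysis section describes regression without saying which readings enter or how readings from one patient are related.

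Two things are at stake. First, if the analyst takes one 12-month reading per patient, the printed detectable differences are too optimistic for that analysis. Second, the primary SBP analysis is left open: 12-month level, change from baseline or pooled visits, each adjusted or not, all fit the text. That choice should not remain for after the data are seen.

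**Working it through.** **Inputs.** From Section 9.3: SD 20, type I error 0.05, power 80%, correlation 0.2, ICC 0.0085, effective n 147 per arm, 250 enrolled per arm, attrition 20% or 30% (so 200 or 175 per arm remain). Sidedness is not stated; two-sided is assumed, so z = 1.960 + 0.842 = 2.8016. The 8 mm Hg is from Section 1.1. Results below are given as 20% / 30% attrition.

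**1. The plan's own figure.** For m readings per patient with exchangeable correlation ρ, the detectable effect in SD units is d = 2.8016 × √(2[1 + (m−1)ρ] / (m n)).
- m = 2.6, n = 147, ρ = 0.2: √(2 × 1.32 / 382.2) = 0.0831, so d = 0.233 or 4.66 mm Hg. Printed: 0.215 (4.29).
- m = 2.4: √(2 × 1.28 / 352.8) = 0.0852, so d = 0.239 or 4.77 mm Hg. Printed: 0.253 (5.06).

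On these inputs, power at the printed effects is about 73% and 84%. A one-sided test gives 0.207 and 0.212, which does not match either. With n fixed at 147, the two effects can differ by a factor of at most √(2.6/2.4) = 1.04 for any ρ ≥ 0, but the printed pair differs by 0.253/0.215 = 1.18. No single correlation and type I error gives both. The 0.253 is reproduced by m = 2 (0.2531), which is not the stated 2.4.

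The counts 2.6 = 1 + 0.8 + 0.8 and 2.4 = 1 + 0.7 + 0.7 include baseline, which cannot carry a treatment effect.

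**2. One unadjusted 12-month SBP per patient.** Detectable difference = 2.8016 × 20 × √(2/n).

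| Case | n per arm | Detectable, mm Hg | Power at printed 4.29 / 5.06 | Power at 8 mm Hg |
|---|---|---|---|---|
| No site effect | 200 / 175 | 5.60 / 5.99 | 57% / 66% | 98% / 96% |
| Plan's effective n | 147 | 6.54 | 45% / 58% | 93% |
| Completers, full site design effect | 108.6 / 100.9 | 7.60 / 7.89 | 35% / 44% | 84% / 81% |

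The last row divides 200 by 1 + 99 × 0.0085 = 1.84, and 175 by 1 + 86.5 × 0.0085 = 1.74. It is a pessimistic bound, because patients are randomised within site.

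**3. Change from baseline (a Table 1 form).** At correlation 0.2 the SD of change is 20 × √(2 × 0.8) = 25.3. Unadjusted power at 8 mm Hg is 88.5% / 84.1% without a site effect and 64% / 61% with the full design effect.

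**4. Baseline-adjusted 12-month SBP.** The residual SD is 20 × √(1 − r²). With no site effect and r = 0.2, 0.5 or 0.7 (assumed for the baseline-to-12-month correlation), the detectable difference is 5.49 / 5.87, 4.85 / 5.19 or 4.00 / 4.28 mm Hg.

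**5. Pooling the 3- and 12-month readings.** If standard errors ignore the patient, they are too small by √(1 + ρ), and the true type I error is 2[1 − Φ(1.96/√(1 + ρ))]: 7.4% at ρ = 0.2 and 11.0% at ρ = 0.5 (assumed).

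**The case against.** Several points can fairly be made for the plan.

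- **Silence is not exclusion.** A reader might infer that Section 9.5 analyses one visit only and that the 3-month SBP is never used. The text does not say so. It names no time point and does not limit the data to one record per patient. What stands is that no role is stated.
- **Type I error.** A reader might infer that pooling would inflate it. That follows only if the standard errors ignore the patient. Patients are nested in sites, so a sandwich estimator clustered on site would also absorb within-patient correlation. Section 9.5 does not state the clustering level. Clustering on four sites brings its own difficulty: in simulation (400 patients, four sites, two readings each, site dummies) the type I error was about 14% with normal critical values and about 5% with t on 3 degrees of freedom. Inflation is possible but not prescribed.
- **Dropout.** Patients without a 12-month reading are not ignored. Section 9.5 provides attrition weights if needed, and Section 6.2.3 plans an attempt at the final outcome survey on withdrawal.
- **Size of the gap.** The 5.60 and 5.99 carry no site effect, whereas the printed values use an effective size after clustering. The printed values also fail to reproduce. The difference therefore cannot all be put down to the model mismatch, and baseline adjustment would narrow it.
- **The trial's target.** The hypothesis is 8 mm Hg, for which a comparison of 12-month SBP keeps 81% to 98% power.

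These points limit the consequences. None supplies the missing model, and the mismatch between the two sections stands.

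**Conclusion.** The power model and the analysis model do not match, and Section 9.5 does not define the primary SBP analysis. For one unadjusted 12-month SBP per patient, the detectable difference is 5.60 / 5.99 mm Hg without a site effect and 6.54 mm Hg at the plan's effective n, against the printed 4.29 / 5.06. This assumes SD 20, a two-sided 5% test and 80% power. Aligning the models would not be enough, because the printed figures do not follow from their own inputs.

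A reader might conclude that the trial is underpowered. The documents do not support that for the 8 mm Hg hypothesis when follow-up SBP is compared. Power falls below 80% for an unadjusted change score at correlation 0.2 once clustering is allowed for, to 61% to 64% with the full site design effect. Adequacy therefore depends on the choice that Section 9.5 leaves open. The demonstrated defects are a wrong stated figure, an unspecified primary analysis and a possible efficiency gain from the 3-month reading that the plan does not secure.

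**What to change.** 1. In Section 9.5, name one primary SBP analysis with the 12-month arm difference as the primary estimate. One suitable choice is a linear mixed model on the post-randomisation examination visits, with arm by visit, baseline SBP by visit, site and an unstructured within-patient covariance. A baseline-adjusted regression of 12-month SBP would also align the sections, but without using the 3-month reading.
2. State how the overall weight enters that model and, wherever sandwich errors remain, the level of clustering.
3. Reconcile whether SBP is examined at 8 months: the Section 6.1 schedule marks it, while the Synopsis data sources and Section 9.3 list only baseline, 3 and 12 months.
4. Keep the regression models for outcomes analysed at one visit, including the share of patients below 120/80.
5. Recompute and restate the Section 9.3 detectable difference for the 12-month contrast. State the sidedness and the derivation of the effective size, and do not count baseline as an outcome reading.

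The cost is wording and a recalculation, with no new data. The stated detectable difference may become less favourable.

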- *Declining consent:* If patients do not consent to the study, the RA will record the reason why the patient did not consent. Further, the RA will ask permission to use the demographic information of the patient to generate enrollment propensity weights. Enrollment propensity weights will be used to analyze how the tendency to participate in the RCT impacts attainment of outcomes.
- *Storing consent forms.* The consent forms at each site will be stored in a locked file cabinet within a locked room. Access is limited to the site's Principal Investigator and research staff.

For the baseline survey, the RA will enter the circumstances of the initial visit (inpatient/outpatient, whether clinical team called RA or subject, reasons for ineligibility, and reasons for nonparticipation). These data will be summarized in a monthly report by site and shared among the Task Force and the research teams at UCLA and at each site.

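### The intention-to-treat models carry an enrollment weight that the randomized comparison does not need, that no stated estimand calls for, and whose variance is not in the power calculation

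*Combined protocol and SAP*

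**What the plan says.** Section 9.5 (Data Analyses) defines two weights. The first is unconditional: "Enrollment weights based on a logistic regression model will be calculated using demographic data collected from eligible non-participants". The second, for attrition, is to be derived only if needed. The two are merged into one overall weight, the inverse of the product of the participation probabilities. Intention-to-treat analyses of every primary and secondary outcome are then fitted "using ordinal logistic or multiple linear regression models, incorporating the overall weight". The same section adds a descriptive comparison: "Both raw and adjusted rates using the overall weight will be compared between SUCCEED and usual care arms".

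The data for the enrollment weight come from section 4.3.3. When a patient declines, "the RA will ask permission to use the demographic information of the patient to generate enrollment propensity weights". That section states what the weights are for: studying how the tendency to take part affects attainment of outcomes.

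Section 4.3.4 places consent and baseline data collection before randomization. Section 9.3 (Power Analysis) allows for site clustering, attrition, repeated measurements and autocorrelation. It has no term for weighting.

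**The concern.** Weighting for enrollment answers a different question from the one randomization answers. Whether a patient enrolled is settled before the arm is known, so participation cannot confound the arms, and the unweighted contrast is already unbiased for randomized patients. The enrollment weight redirects the estimate toward eligible patients in general. That can be a legitimate target, but the plan does not state it as one.

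Three things are at stake:

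- **Estimand.** The main result would describe a population that the objectives and hypotheses do not define.
- **Dependence on a participation model.** The estimate would rest on a logistic model fitted to demographics from a selected group of decliners.
- **Precision.** Unequal weights raise the variance of the arm difference, and section 9.3 does not budget for this.

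**Working it through.** **1. Reproduce the plan's figures, to see whether weighting is included.**

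Inputs from section 9.3: "mean SBP 141 mm Hg and standard deviation (SD) 20"; ICC 0.0085; 250 per arm; autocorrelation 0.2; type I error 0.05 (taken as two-sided, which reproduces the figures); power 80%, so z = 1.960 + 0.842 = 2.802.

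- Effective n per arm = 250 / [1 + (250/k − 1) × 0.0085], with k sites. With k = 3: 250 / 1.6998 = 147.07, the stated 147. With k = 4: 250 / 1.5228 = 164.2.
- Variance factor v for the mean of m measurements under first-order autoregression. For m = 3: (3 + 4×0.2 + 2×0.04)/9 = 0.4311. For m = 2: (2 + 2×0.2)/4 = 0.6.
- Detectable difference = 2.802 × 20 × √(2v/147) = 4.29 mm Hg (m = 3) and 5.06 mm Hg (m = 2), as stated for 20% and 30% attrition.

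The figures reproduce with no weighting factor, so that variance is absent. Two side observations: 147 needs three sites although section 9.3 refers to four centers (section 9.5 also says "the three sites are part of the same county healthcare system"), and the stated 2.6 and 2.4 data points appear to have been used as 3 and 2.

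**2. Add the enrollment weight.**

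For weights unrelated to SBP, variance rises by about 1 + CV² and the detectable difference by its square root. The documents give no CV, so 0.3, 0.5 and 0.7 are assumptions. Power for the 8 mm Hg hypothesized in section 1.1 is Φ(8/SE − 1.96), with SE = 20 × √(2v(1 + CV²)/147).

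| Assumed CV | 1 + CV² | Detectable, 20% / 30% attrition (mm Hg) | Power for 8 mm Hg, 20% / 30% attrition |
|---|---|---|---|
| 0 | 1.00 | 4.29 / 5.06 | 99.9% / 99.3% |
| 0.3 | 1.09 | 4.48 / 5.28 | 99.9% / 98.9% |
| 0.5 | 1.25 | 4.80 / 5.66 | 99.7% / 97.7% |
| 0.7 | 1.49 | 5.24 / 6.18 | 99.0% / 95.2% |

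The detectable difference reaches 8 mm Hg only at a CV of about 1.57 (20% attrition) or 1.22 (30%).

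A simulation with about 400 randomized patients and weights unrelated to SBP agreed with the formula. Both estimators were unbiased, and the variance ratio was 1.12 at CV 0.34 (formula 1.12) and 1.55 at CV 0.73 (formula 1.53).

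**3. Check the slack if the model is a single 12-month regression.**

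Section 9.5 names ordinal logistic or multiple linear regression, and the hypothesis is set at 1 year. With 30% attrition, n = 250 × 0.7 = 175 per arm.

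- Unweighted: 2.802 × 20 × √(2/175) = 5.99 mm Hg. At CV 0.7: 5.99 × √1.49 = 7.31 mm Hg.
- With the plan's clustering factor: 5.99 × √1.6998 = 7.81 mm Hg. At CV 0.25: 7.81 × √1.0625 = 8.05 mm Hg.

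**4. Check who supplies the weights.**

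Decliners who refuse permission contribute nothing. Under section 4.3.1 a clinician must first obtain the patient's verbal agreement before passing on a name, so patients never referred are missing too, unless they called the study themselves. No permission or referral rate is given, so the size of this selection is unknown.

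**The case against.** The strongest defense is that weighting to the eligible population is a recognized way to seek generalizability. This trial has a county-system perspective, a sustainability aim and a list of expected moderators. Section 9.5 also specifies sandwich standard errors, which would reflect the variance from the weights. All of that stands, and it rules out a validity defect. It does not supply the missing estimand, and it does not explain why weights meant for studying the tendency to participate sit in the main models.

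A reader might infer more than the documents support:

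- **That the trial falls below 80% power.** Power of 77% / 71% / 63% at CV 0.3 / 0.5 / 0.7 is correct at 4.29 mm Hg, but that is the smallest detectable difference, not the hypothesized 8 mm Hg. The CVs are also assumed, and nothing in the documents shows that demographics-only weights would vary that much.
- **That no rule says whether the raw or the weighted result counts.** Section 9.5 specifies the weighted model as the intention-to-treat model. The raw comparison concerns rates, and no unweighted model is named.
- **That the weights misrepresent non-participants.** Without a permission rate, the text supports only that they may.

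It is also fair to say that the 1.70 clustering factor is conservative for patients randomized individually within site strata, with site terms in the model. It exceeds the largest weighting factor shown here, 1.49.

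**Conclusion.** The point holds as one of precision and estimand. The enrollment weight is unnecessary for an unbiased comparison of arms, serves no stated population estimand, may rest on unrepresentative data, and adds variance that section 9.3 omits.

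At assumed CVs of 0.3 to 0.7, the detectable difference grows by about 4% to 22% (√1.09 to √1.49). On the plan's repeated-measures set-up this leaves power for 8 mm Hg at about 95% or more. The margin is smaller for a single 12-month regression, where at 30% attrition the unweighted detectable difference is already about 6.0 mm Hg, or 7.8 with the 1.70 factor.

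These sizes rest on the assumed CVs, on weights unrelated to SBP, on SD 20, and on taking the plan's 147 per arm as given. The documents do not support a claim of inflated type I error or of an underpowered trial. The change is worth making because it costs little and removes an avoidable dependence.

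**What to change.** In section 9.5:

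1. Define the primary intention-to-treat model without enrollment weights: all randomized participants by assigned arm, adjusted for baseline SBP and the stratification factors (site, language, stroke type).
2. Handle attrition separately, by attrition weights or another prespecified missing-data method. Dropout follows randomization, so this part can be justified on its own.
3. Keep the enrollment-weighted estimate as one prespecified sensitivity analysis of generalizability, in line with the purpose in section 4.3.3. Report how many decliners gave permission.

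The cost is wording only. Baseline SBP and the stratification factors are already collected, and decliner demographics would still be gathered. The downsides are that the primary estimate refers to enrolled patients, and that any attrition weighting kept in the primary model still costs some precision.
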